2.2. Study Objective(s) and Endpoint(s)

Objectives	Endpoints
Primary Objectives	Primary Endpoints

 To determine safety, tolerability, maximum tolerated dose (MTD), and recommended phase (RP2) dose and schedule of GSK2857916 administered 	
 Adverse events (AE) and changes in clinical signs and laboratory parameters
Secondary Objectives	Secondary Endpoints

 To evaluate the pharmacokinetic (PK) profile of GSK2857916 and the breakdown product cys-mcMMAF after intravenous (IV) single and repeat dose administration in subjects with relapsed/refractory MM and BCMA expressing lymphomas 	
 GSK2857916 and cys-mcMMAF PK parameters following IV single and repeat dose administration during dose escalation as data permit (e.g., AUCs C_{max}, t_{max}, CL, V_{ss}, t_{1/2} [single dose], C_{max} and C_{trough} [repeat dose]). GSK2857916 population PK parameters in expansion cohorts at the RP2 dose (e.g. clearance (CL), volume of distribution (V_d)), and relevant covariates which may influence exposure (e.g. age, weight, or disease-related covariates e.g. BCMA expression)

 To assess anti-drug antibody (ADA) formation after IV single and repeat dose administration of GSK2857916 	
 ADA incidence and titers after single and repeat IV dosing of GSK2857916

 To explore the initial anti-tumor activity of GSK2857916 in subjects with relapsed/refractory MM and BCMA expressing lymphomas 	
 Clinical activity measured as Overall Response Rate (ORR) which is defined as follows: 
 For MM: the percentage of subjects achieving confirmed partial response or better (≥PR) In addition, the percentage of subjects with minimal response (MR) will be assessed for clinical benefit rate (CBR) (Appendix 1 of protocol) For Lymphomas: the percentage of subjects achieving PR or better (≥PR) (Appendix 2 of protocol)
Exploratory Objectives	Exploratory Endpoints

 To evaluate PD markers in MM after treatment with GSK2857916 	
 sBCMA levels, BCMA receptor occupancy and cell death markers in subjects with MM.

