14. ANTI-DRUG ANTIBODY ANALYSES

For each subject, the results and titers of anti-GSK2857916 binding antibodies, and also ADC and total antibody concentration will be listed for each assessment time point. The frequency and percentage of subjects with positive and negative results will be summarized for each assessment time and overall for each subject by dose cohort. The conclusive results will be based on the total antibody concentration.

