AVALC	POSITIVE	POSITIVE	1																													
AVALC	POSITIVE	NEGATIVE	0																													
AVALC	POSITIVE	MISSING	-99																													
AVALC	MISSING	ANY	-99																													
IMM	Overall Immunogenicity Outcome 0=anti-GSK3174998 negative, 1=anti-GSK3174998 positive (at least one postdose)	0 = negative 1 = positive -99 = missing	
 • If IMMU = 1 at any observation for a subject, IMM = 1 • else if all IMMU = -99, IMM = -99 
Else IMM = 0
 
Fill in IMM in all rows for each subject
																													

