	X mg/kg (N=X)

Number of subjects with baseline ADA results	X (X%)
Number of subjects with negative baseline ADA results	X (X%)
Number of subjects with confirmed positive baseline ADA results	X (X%)
Number of subjects with post-baseline ADA results	X (X%)
Number of subjects with at least one confirmed positive post-baseline ADA result	X (X%)
Number of subjects with all negative post-baseline ADA results and at least one GSK2857916 total antibody concentration \leq 25000 ng/mL	X (X%)
Number of subjects with all negative post-baseline ADA results and all GSK2857916 total antibody concentration $>$ 25000 ng/mL	X (X%)

[figure not shown]
Note a subject is considered to have a positive ADA result if they have a positive screening assay, a positive confirmation assay and a titer value.

PPD

Example: SAFE_F1
 Protocol: BMA117159
 Population: Part 1

Page 1 of 1
 (Data as of: 30MAY2001)

Figure x.xxxx
 Proportions of Subjects with Infusion-related Reactions (Part 1)

[figure not shown]

PPD

Example: SAFE_F2
Protocol: BMA117159
Population: All Treated MM

Page 1 of 1
(Data as of: 30MAY2001)

Figure x.xxxx
Profile plot for patients with No Corneal Event or Grade 1 Corneal Event (Part 2 MM)

a. sCR: Stringent Complete Response, CR: Complete Response, VGPR: Very Good Partial Response, PR: Partial Response, MR: Minimal Response, SD: Stable Disease, PD: Progressive Disease, NE: Not evaluable.
b. Dose reduction/delays can be due to non-corneal AEs.

PPD

Example SAFE_L1
Protocol: BMA117159
Population: Part 2 MM

Page 1 of 1
(Data as of: 30MAY2003)

Listing x.xxxx

Listing of Disease Characteristics, Prior Treatment, Dose Modification and Response to GSK2857916
(Part 2 MM)

Part: 2
Treatment: 3.40 MM

Centre ID/ Subj.	ISS Stage at Screening	Number of Prior Lines of Therapy	Refractory to Last line of Therapy	Prior Daratumumab?	Refractory to both IMiDs and Proteasome Inhibitors?	Best Confirmed Response
PPD	III	6 Lines	Yes	Yes	Yes	Progressive disease
	II	7 Lines	Yes		Yes	Very Good Partial Response (VGPR)
	I	8 Lines	Yes		Yes	Very Good Partial Response (VGPR)

PPD

CONFIDENTIAL

BMA117159

Example SAFE_L2
 Protocol: BMA117159
 Population: All Treated MM

Page 1 of 1
 (Data as of: 30MAY2003)

Listing x.xxxx
 Listing of Visual Acuity and Abnormal Corneal Exam Results

Part 1
 Treatment: 0.01 mg/kg

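### The PopPK overall ADA flag counts pre-dose positives against its own label, and the ADA summary tables cannot show how many subjects formed antibody on treatment

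*SAP*

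**What the plan says.** **Objective and endpoint (SAP Section 2.2).** The objective reads "To assess anti-drug antibody (ADA) formation after IV single and repeat dose administration of GSK2857916". The endpoint is "ADA incidence and titers after single and repeat IV dosing of GSK2857916". Section 14 plans positive and negative frequencies "summarized for each assessment time and overall for each subject by dose cohort" and sets no rule for subjects who are positive at baseline.

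**Summary table (Appendix 13, SAFE_T5).** Appendix 13 appears twice in the SAP text. In both copies of this shell there is a row "Number of subjects with confirmed positive baseline ADA results" and, further down, a row "Number of subjects with at least one confirmed positive post-baseline ADA result". No row combines them. The footnote calls a subject's result positive, in its words "positive ADA result if they have a positive screening assay, a positive confirmation assay and a titer value"; it asks for no rise over a baseline titer. One copy also defines the baseline sample as the closest one before first dose, but neither uses baseline status to classify later positives.

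**PopPK dataset (Section 16.9.1).** The overall flag IMM is labelled "positive (at least one postdose". Its derivation is "If IMMU = 1 at any observation for a subject, IMM = 1". The underlying variable IMMU is set by collection time and imputed between ADA visits. When it goes from positive to negative, it stays positive on every record before the first known negative.

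**The concern.** A programmer cannot satisfy both the label and the rule for IMM. Following the rule, a subject whose only positive sample predates treatment is flagged positive in a variable that its label reserves for post-dose positivity. Section 16.9.2 names immunogenicity status among the candidate PopPK covariates, so the misclassification could enter the covariate analysis.

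For SAFE_T5 the issue is what the table can answer. Formation means going from no antibody to antibody. Two uncrossed margins do not identify that number once anyone is positive at baseline, and this is the only per-subject count of post-baseline positives in the planned ADA summaries. The other table shell, SAFE_T4, gives counts visit by visit.

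**Working it through.** The SAP states no ADA rate, so there is no figure to reproduce. The check is textual first, then a bound.

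**1. Can a pre-dose positive reach IMM?**
- Pre-first-dose ADA samples exist. On the every-3-week schedules in Appendix 2, ADA is drawn at screening in Part 1 and on Cycle 1 Day 1 in Part 2 (MM and lymphoma). ADA samples are taken before infusion.
- Pre-dose rows exist in the PopPK dataset: Section 16.9.1 assigns pre-dose samples a nominal time of 0.
- The IMM rule has no post-dose restriction, so a pre-dose IMMU of 1 is enough.

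**2. Would restricting IMM to post-dose records be sufficient?** No. Take a subject positive before dose 1 and negative at Cycle 2 Day 1. The IMMU imputation keeps the value at 1 on all PK records in between. In Part 1 these include the Day 1 post-infusion, Day 2, Day 8 and Day 15 samples; in Part 2 MM, the end-of-infusion sample. Post-dose records then carry a 1 that no post-dose assay produced.

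**3. What do the SAFE_T5 margins identify?** Let N be subjects with both a baseline and a post-baseline result, b the baseline positives and m those with any post-baseline positive.
- Treatment-induced count: from max(0, m − b) to min(m, N − b), out of N − b baseline-negative subjects.
- IMM = 1 under the written rule: from max(b, m) to min(N, b + m). Under the label, counting assayed post-dose positives: m.

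N = 40 is the maximum size of the MM expansion cohort (Section 3.1.2.1.1). The values of b and m are assumptions, because the SAP gives neither.

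| b | m | SAFE_T5 shows | Treatment-induced | IMM = 1, rule | IMM = 1, label |
|---|---|---|---|---|---|
| 0 | 3 | 3/40 = 7.5% | 3/40 = 7.5% | 3 | 3 |
| 2 | 3 | 3/40 = 7.5% | 1 to 3 of 38 = 2.6% to 7.9% | 3 to 5 | 3 |
| 4 | 4 | 4/40 = 10.0% | 0 to 4 of 36 = 0% to 11.1% | 4 to 8 | 4 |

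For the second row: max(0, 3 − 2) = 1 and min(3, 38) = 3, so 1/38 = 2.6% and 3/38 = 7.9%; IMM runs from max(2, 3) = 3 to min(40, 5) = 5. With b = 0 nothing changes. With b above 0, one table count fits several answers, and the IMM rule can flag up to b subjects more than its label allows.

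**The case against.** **SAFE_T5 misstates nothing.** Its row says post-baseline positive, not treatment-emergent or induced, and a count of post-dose positives is a literal reading of the endpoint. Baseline positives are displayed in the same table. Listing SAFE_L3 (Listings 30.0620 and 30.0621) gives screening assay, confirming assay and titer by visit, so with few positives a reader can sort them by hand. All of this stands. A reader might infer that the plan reports pre-existing antibody as formed on treatment; the shell does not say so. What remains is that the summary tables alone do not answer the stated objective.

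**The bias need not be upward.** A reader might infer that incidence can only be overstated. It cannot be put that way: with baseline-negative subjects as the denominator, 3/38 exceeds 3/40. The SAP also treats negatives with total antibody above 25000 ng/mL as inconclusive, so positives may be missed.

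**The PopPK harm is not demonstrated.** Section 16.9.2 does not say that IMM, rather than the time-varying IMMU, will be the covariate. A reader might infer that an ADA effect on clearance is diluted, but that presumes pre-existing antibody has no PK effect, which nothing in the SAP supports. The analysis is reported separately, and departures from the dataset specification are to be documented.

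**Cycle 1 pre-dose rows may be excluded.** Non-quantifiable or missing pre-dose Cycle 1 concentrations receive an exclusion code in column C. The IMM rule does not refer to that code, however, and the imputed 1 also sits on later records.

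**Conclusion.** Two things are established from the SAP text alone. The IMM label and derivation contradict each other, and under the derivation a subject positive only before first dose is coded ADA-positive; the IMMU imputation also spreads such a positive onto post-dose records until the next negative assay. Separately, the SAFE_T5 margins do not determine how many subjects formed ADA on treatment, although formation is the secondary objective.

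The size is not established. It rests on the baseline-positive rate and on how many baseline positives stay positive, neither of which the SAP gives. It runs from zero, when nobody is positive at baseline, to the ranges in the assumed examples. The direction of any bias in reported incidence, and any effect on PK estimates, cannot be concluded from the document. The point is worth correcting because it concerns a secondary endpoint and the repair is small.

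**What to change.** **Section 16.9.1.** Set IMM = 1 only if an assayed (not imputed) ADA sample collected after the first dose is confirmed positive. Base the negative and missing branches on the same samples, so that a subject with no assayed post-dose result is coded missing. Carry baseline ADA status as a separate variable, since subjects persistently positive from baseline would still be IMM = 1. While editing that cell, correct the compound name, which is given as GSK3174998.

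**SAFE_T5 (Tables 3.0850 to 3.0853).** Keep the present rows and the baseline-sample definition, and add:
- treatment-induced ADA: baseline negative with at least one confirmed positive afterwards, with baseline-negative subjects who have a post-baseline result as the denominator and subjects with missing baseline shown separately;
- baseline-positive subjects whose titer rises after dosing, with the required rise fixed in the SAP before the analysis.

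State in Section 14 that these rows report ADA formation.

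**Cost.** Shell and section wording, one changed derivation line and one carried baseline variable. ADA results and titers are already collected, so no new data are needed.
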